7.3.5. Reporting Serious Adverse Events (SAEs)

The Investigator is responsible for ensuring that all SAEs observed by the Investigator or reported by the subject that occur after signing of the informed consent through 60 days after the last dose of pamrevlumab are recorded in the subject's medical record and are submitted to FibroGen. All SAEs must be submitted to FibroGen within 24 hours following the Investigator's knowledge of the event via the SAE report form. Additionally, pamrevlumab related SAEs (including deaths) that occur after the Safety Follow-up visits will be reported.

If a subject is permanently withdrawn from protocol required therapies because of a serious adverse event, this information must be submitted to FibroGen. FibroGen will report serious adverse events and/or suspected unexpected serious adverse reactions as required to regulatory authorities, Investigators/institutions, and central IRBs/IECs in compliance with all reporting requirements according to local regulations and Good Clinical Practice (GCP).

There is no requirement to monitor study subjects for serious adverse events following the protocol-required reporting period or after end of study. However, these serious adverse events can be reported to FibroGen if the Investigator becomes aware of them. If serious adverse events are reported, the Investigator is to report them to FibroGen within 24 hours following the Investigator's knowledge of the event. Serious adverse events reported outside of the protocol-required reporting period will be captured within the safety database as clinical trial cases for the purposes of expedited reporting; these cases will not be included in the clinical study report.

To report an SAE, the Investigator must complete an SAE Report Form and fax or email the completed form to the Sponsor or its designated safety management vendor.

Full details of the SAE should also be recorded on the medical records and in the CRF. The following minimum information is required:

- Subject number, sex and age
- The date of report
- A description of the SAE (event, seriousness of the event)
- Causal relationship to the study drug

Follow-up information for the event should be sent promptly.

For each SAE observed, the Investigator should obtain all of the information available about the event, including (but not limited to): hospital discharge diagnoses, hospital discharge note, death certificate, appropriate laboratory findings (including autopsies and biopsy results), and clinical examinations (including radiological examinations and clinical consultations).

7.3.5.1. Reporting Serious Adverse Events to the Institutional Review Board / Independent Ethics Committee

The Investigator is responsible for notifying his/her Institutional Review Board (IRB) or Ethics Committee (EC) of SAEs in accordance with local regulations. The Sponsor, or its designated safety vendor, will provide a copy of expedited safety reports to the Investigator that it intends to submit to global regulatory authorities.

7.3.5.2. Deaths

The Investigator will report the fatal event to the Sponsor's medical monitor. The Investigator must provide a causal assessment of the relationship of the event to the study drug according to the guidance in [Section 7.3.4](#).

If the death occurred within the AE collection and reporting period (signed ICF to 60 days after last dose) and meets the reporting criteria, the Investigator must submit the SAE Report Form in the same manner as described above in [Section 7.3.5](#). If the Investigator becomes aware of a death occurring after the AE reporting period and considers it related to pamrevlumab, it will be reported as an SAE.

7.3.6. Pregnancies: Reporting and Follow-up of Subjects and Female Partners of Subjects

The outcome of all pregnancies for female subjects or female partners of male subjects should be followed up and documented as described. If a female subject or a female partner of a male subject becomes pregnant while the subject is receiving study treatment or within 12 weeks after the last dose of study treatment, a Pregnancy Report Form must be completed and submitted to the Sponsor or designated safety management vendor within 24 hours of the Investigator becoming aware of the pregnancy. The Investigator must follow-up to completion of the pregnancy to ascertain its outcome (e.g., spontaneous miscarriage, elective termination, ectopic pregnancy, normal birth or congenital abnormality) and whether any AEs occur during the pregnancy or birth. The outcome of the pregnancy must be reported by the Investigator on a Pregnancy Outcome Report Form, which should be sent to the Sponsor and/or its designated safety vendor within 24 hours of the Investigator becoming aware of the outcome.

Pregnancy itself is not an AE unless there is a suspicion that the investigational product under study may have interfered with the effectiveness of a contraceptive medication. Pregnancies are followed up to outcome even if the subject was discontinued from the study. Congenital abnormalities/birth defects and spontaneous miscarriages should be reported and handled as SAEs. Elective abortions without complications should not be handled as AEs.

If a lactation case occurs while the female subject is taking protocol-required therapies, or within 60 days after the last dose of study treatment, report the lactation case to FibroGen. In addition to reporting a lactation case during the study, investigators should monitor for lactation cases that occur after the last dose of protocol-required therapies through 60 days after the last dose of pamrevlumab. Any lactation case should be reported to FibroGen's Safety within 24 hours of the investigator's knowledge of event.

7.3.7. Laboratory or other Test Abnormalities/ Findings

A laboratory or other test abnormality (e.g., spirometry, HRCT) in the absence of any signs or symptoms is not necessarily an AE. The Investigator must review and assess all test results provided by the central laboratory or other vendors throughout the study in a timely manner, and determine whether any abnormal values/test results are clinically significant (CS) or not clinically significant (NCS), and whether there are associated signs and symptoms. Such abnormalities should be considered CS if they are associated with new signs or symptoms, if they occur after taking study medication, reflect a meaningful change from the screening value(s), or require active management (e.g., requiring treatment, additional testing, study treatment dose modification, discontinuation, more frequent follow-up assessments, etc.).

Clinically significant laboratory abnormalities will be reported as AEs. If the abnormal laboratory finding is accompanied by signs or symptoms, report the signs and symptoms as the AE in lieu of the abnormal laboratory value. If a diagnosis is available, report the diagnosis.

7.3.8. Hypersensitivity/Anaphylactic Reactions:

Hypersensitivity and anaphylactic reactions will be monitored throughout the study, using the criteria below as defined per Sampson et al. 2006 ([Sampson, 2006](#)).

Anaphylaxis is highly likely when the following criteria is fulfilled:

1. Acute onset of an illness (minutes to several hours) with involvement of the skin, mucosal tissue, or both (e.g., generalized hives, pruritus or flushing, swollen lips-tongue-uvula).
And at least one of the following criteria:
 - a. Respiratory compromise (e.g., dyspnea, wheeze-bronchospasm, stridor, reduced PEF, hypoxemia)
 - b. Reduced BP or associated symptoms of end-organ dysfunction (e.g., hypotonia [collapse], syncope, incontinence)
2. Two or more of the following that occur rapidly after exposure to a likely allergen for that patient (minutes to several hours):
 - a. Involvement of the skin-mucosal tissue (e.g., generalized hives, itch-flush, swollen lips-tongue-uvula)

- b. Respiratory compromise (e.g., dyspnea, wheeze-bronchospasm, stridor, reduced PEF, hypoxemia)
 - c. Reduced BP or associated symptoms (e.g., hypotonia [collapse], syncope, incontinence)
 - d. Persistent gastrointestinal symptoms (e.g., crampy abdominal pain, vomiting)
3. Reduced BP after exposure to known allergen for that patient (minutes to several hours):
- a. Systolic BP of less than 90 mm Hg or greater than 30% decrease from that person's baseline

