- For on-study laboratory assessments, only laboratory abnormalities that are considered clinically significant in the Investigator's assessment need to be reported as TEAEs, as per Protocol Section 7.3.7. In such a case, if possible, the etiology of a lab abnormality should be reported as TEAE, not the abnormal lab value.
- For specialty labs, please collect HAHA samples according to the SOA in Appendix 2 using local supplies while processing/storing these samples as described in the ICON lab manual. Other specialty samples (PK, Biomarkers, Genomic and CTGF) will not be required if local labs are being used

Note: For Czech Republic only, Tuberculosis (TB) screening test to be done using site local lab, if this test was not performed within 6 months prior to screening per study exclusion criteria 23.

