7.3.2. Adverse Event Eliciting/Reporting

During the AE reporting period, study site personnel will actively seek information from each subject at each visit to collect any AEs occurring since the previous visit. All AEs will be collected in response to a general question about the subject's well-being and any possible changes from the BL or previous visit. There will be no directed questioning for any specific AE. This does not deter the site from collecting and recording any AEs reported by the subject to site personnel at any other time.

Whenever possible, diagnoses should be recorded when signs and symptoms are due to a common etiology, as determined by qualified medical study staff. The Investigator is responsible for reviewing laboratory test results and determining whether an abnormal value in an individual study subject represents a clinically significant change from the subject's baseline values. In general, abnormal laboratory findings without clinical significance (based on the Investigator's judgment) are not to be recorded as adverse events. However, laboratory value changes that require treatment or adjustment in current therapy are considered adverse events. Where applicable, clinical sequelae (not the laboratory abnormality) are to be recorded as the adverse event. The Investigator is expected to follow reported adverse events until stabilization or reversibility.

The following attributes must be assigned to each AE:

- Description (Investigator's verbatim term describing the event)
- Dates of onset and resolution
- Severity
- Relationship to study drug
- Outcome
- Action taken regarding study drug
- Other treatment required
- Determination of "seriousness"

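### Protocol 7.3.7 lets timing after study medication alone make a laboratory abnormality clinically significant, and so an AE, in conflict with 7.3.2, 6.2.4.1 and the OLE note

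*Protocol*

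**What the plan says.** Protocol Section 7.3.7 opens by saying that a laboratory or other test abnormality "in the absence of any signs or symptoms is not necessarily an AE". It asks the Investigator to classify each abnormal result as clinically significant (CS) or not (NCS). It then gives the test: "Such abnormalities should be considered CS if they are associated with new signs or symptoms, if they occur after taking study medication". The list continues with abnormalities that "reflect a meaningful change from the screening value(s), or require active management". The next paragraph states the consequence, "Clinically significant laboratory abnormalities will be reported as AEs", with one substitution rule: where there are signs or symptoms, "report the signs and symptoms as the AE in lieu of the abnormal laboratory value", and where there is a diagnosis, report that.

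Other sections set a different standard:

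- Section 7.3.2 has the Investigator judge whether a value is a clinically significant change from that subject's baseline. It says that "abnormal laboratory findings without clinical significance (based on the Investigator's judgment) are not to be recorded as adverse events", but that changes needing treatment or an adjustment of therapy are AEs.
- Section 6.2.4.1, for local laboratories used in place of the central one, says that "only laboratory abnormalities that are considered clinically significant in the Investigator's assessment need to be reported as TEAEs", and cites 7.3.7 as its authority.
- Appendix 6, note k to the OLE Schedule of Assessments, tells sites not to report laboratory abnormalities that lack clinical significance.

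**The concern.** The four alternatives in 7.3.7 are joined by "or", so any one is sufficient. One of them is only that the abnormality arose after study medication was taken. Every result that could become a treatment-emergent event meets that condition, so on the wording no post-dose laboratory abnormality can be NCS. The Investigator's judgment, on which 7.3.2 and 6.2.4.1 rely, then has nothing left to decide.

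What is at stake is consistency of safety reporting. The synopsis plans about 170 sites. If some apply the literal list and others apply 7.3.2, the same laboratory value is an AE at one site and not at another, and laboratory AE incidence partly reflects which section was followed.

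**Working it through.** The plan states no figure that could be reproduced here. The check is to take typical post-dose laboratory abnormalities and apply each rule in turn.

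| Post-dose laboratory abnormality | 7.3.7, read literally | 7.3.2 | Double-blind SAP 6.8.1 |
|---|---|---|---|
| A. Already abnormal at screening, unchanged, no symptoms, no action | CS by timing, so AE | Not an AE if judged not significant | Not new or worsening, so not a TEAE |
| B. Newly out of range, small change, no symptoms, no action | CS by timing, so AE | Not an AE if judged not significant | New, so a TEAE if reported; one count per subject per preferred term |
| C. Clinically significant change in the Investigator's judgment | AE | AE | TEAE |
| D. Needs treatment or a change in therapy | AE | AE | TEAE |
| E. With signs, symptoms or a diagnosis | AE, recorded as the symptom or diagnosis | AE, recorded as the diagnosis or clinical sequelae where applicable | TEAE |

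(C to E assume a new or worsening event.)

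1. The rules agree on C, D and E. These are also the cases that the other three alternatives in 7.3.7 cover without help from timing.
2. They disagree on A and B, and in both rows the timing alternative alone produces the disagreement.
3. Row A is an AE-reporting conflict that should not reach the TEAE tables. Section 7.2.1 also says that a pre-existing condition that has not worsened is not an adverse event. Row B can reach the tables.
4. Section 7.3.1 already confines non-serious AE reporting to the period from the first dose. Timing is therefore handled by the reporting period, and the extra limb is not needed for that purpose.
5. With the timing limb removed, A and B meet none of the remaining alternatives and become NCS, in agreement with 7.3.2. Rows C to E do not change.

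**The case against.** The strongest reply is that the protocol, read as a whole, leaves the decision to the Investigator. Section 7.3.7 itself asks for a CS or NCS decision. Section 6.2.4.1 cites 7.3.7 for a test based on the Investigator's assessment and gives review of central results to the Investigator. Section 7.3.2 and the OLE note agree. On this view one badly built clause does not override several consistent statements, and experienced sites will not apply it literally. This stands in part: the protocol is ambiguous rather than uniformly over-inclusive. It does not remove the conflict, because the clause says when results should be considered CS and a site that follows it is complying with the protocol.

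A reader might go further and infer any of the following, which the documents do not support:

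- *That incidental values would swamp the TEAE tables.* The new-or-worsening rule, the single count per preferred term and the substitution of symptoms or a diagnosis all reduce the effect.
- *That a real laboratory signal would be hidden.* The double-blind SAP analyses laboratory data directly in 6.8.3 (values, changes from baseline, toxicity grades, shift tables) and 6.8.4 (liver thresholds and an ALT/AST against bilirubin plot). Neither depends on AE reporting.
- *That a site following 7.3.2 would report hardly anything.* Significant changes and those needing treatment are AEs there too.
- *That spirometry and HRCT findings become AEs.* The CS test covers them, but the automatic AE step is limited to laboratory abnormalities.

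**Conclusion.** The contradiction is real and comes from one clause. On its wording, 7.3.7 makes post-dose timing sufficient for clinical significance and hence for AE reporting of laboratory abnormalities. That cannot be squared with its own CS/NCS decision, with 7.3.2, with 6.2.4.1 or with the OLE note. The supportable consequence is inconsistent reporting between sites for abnormalities without symptoms, meaningful change or intervention (rows A and B), and some added noise in laboratory AE incidence. The plan gives no reason to expect this to differ between blinded arms, and it does not affect the efficacy analysis or the sample size.

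The size cannot be stated. It is tempting to multiply the 33 laboratory lines of Table 2 (14 + 19) by the post-dose panels and an assumed out-of-range rate. The documents give no such rate. Related tests, such as ANC and neutrophils, and repeated tests in one subject are not independent, and a persistent abnormality is not a new AE at each visit. Even the number of panels varies: five (33 × 5 = 165 results) for a completer who does not enter the OLE, but four (33 × 4 = 132) in the main phase for one who does, because the 28-day visit then follows the last OLE dose. The conclusion rests on the wording alone and on the assumption that at least some sites would apply the clause as written.

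**What to change.** Reconcile 7.3.7 with 7.3.2, 6.2.4.1 and the OLE note. Either delete the timing alternative, or make it joint, so that an abnormality arising after study medication must also show a meaningful change from the screening value. Keep the other alternatives. Symptomatic, meaningfully changed and actively managed abnormalities then remain reportable, and the NCS category regains its meaning.

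The edit is one clause, but it is a protocol amendment: Section 10.2 requires written IRB/IEC approval before an amendment is implemented, and sites need a short memo. No change to the SAP is needed.

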7.3.9. Safety Monitoring

Safety will be assessed throughout the study. A medically complete baseline profile of each subject will be established through medical history, a complete physical examination including vital signs, laboratory tests, PFTs, and a 12-lead ECG. During the course of the study, vital signs, laboratory tests, and PFTs will be performed at frequent intervals as described in [Appendix 1](#) and [Appendix 2](#). Any medically significant changes from baseline will be monitored throughout the study and appropriate interventions will be taken accordingly. Safety and tolerability will be monitored closely by FibroGen.

7.3.9.1. Special Reporting Situations

Special Reporting Situations on FibroGen investigational product pamrevlumab (or placebo) that require safety evaluation include:

- Overdose (any dose greater than 4.1g)
- Suspected abuse/misuse
- Inadvertent or accidental exposure
- Medication error (e.g. incorrect dose administered)
- Drug-drug interactions

Report special situations to FibroGen's Safety within 24 hours of the investigator's knowledge of the event. See Study Reference Manual for detailed reporting instructions.

7.3.9.2. Data Monitoring Committee (DMC)

A Data Monitoring Committee (DMC) will be utilized and will be composed of external experts. Composition and responsibilities of the DMC will be defined in a separate DMC charter. The DMC responsibilities will include review of the safety data.

8. STATISTICS

8.1. Sample Size Determination

This study will enroll approximately 340 subjects with a 1:1 randomization ratio to pamrevlumab or placebo, respectively.

A sample size of 340 subjects will have at least 90% power, based on a two-sided alpha level of 0.05 for a two-sample t-test, to detect a treatment difference of 120 mL in the primary efficacy endpoint, change from baseline in FVC (L), assuming a common standard deviation of 300 mL. This sample size allows for a dropout rate of approximately 20%.

The rationale for these sample size assumptions are as follows. In the phase 2 study FGCL-3019-067, a treatment difference of 178 mL was observed in change from baseline in FVC to Week 48. For this study, a conservative treatment difference of 120 mL is assumed. The standard deviation is estimated based on published results from other IPF studies.

8.2. Analysis Populations

8.2.1. Intent to Treat (ITT) Population

The ITT population is defined as all randomized subjects. Subjects will be analyzed according to the treatment as randomized.

8.2.2. Safety Population

The safety population is defined as all subjects who have received the study medication. Subjects will be analyzed according to the treatment as received.

8.3. Statistical Analysis

8.3.1. General Considerations

The primary efficacy endpoint will be tested at the significance level of 0.05 (2-sided). Upon observing a significant treatment difference in the primary endpoint, the secondary endpoints will be tested sequentially in a fixed sequence according to the order listed in section 3.2.2, taking into consideration the adjustment for the family-wise error-rate of 0.05 (2-sided). The testing will continue with the significance level of 0.05 (2-sided) in sequential fashion until the test fails to show statistical significance for a secondary endpoint.

Baseline characteristics, safety, efficacy, and biomarker data will be summarized by treatment arm, based on available data in the ITT and/or Safety Population.

All study parameters will be presented in the data listings and summarized descriptively by visit. Descriptive statistics for continuous variables include: n, mean, standard deviation or standard error, median, minimum, and maximum. Categorical variables will be presented by frequency count of subjects and percentage. Two-sided 95% confidence intervals will be provided.

Efficacy and safety analyses for treatment arm (pamrevlumab vs placebo) comparisons will only be based on data observed during the main study that is double-blind and placebo-controlled. Data from the OLE period will be summarized descriptively.

8.3.2. Subject Enrollment and Disposition

The number (%) of subjects who completed or discontinued the study, and reasons for early discontinuation, will be summarized by treatment for subjects in the ITT population.

8.3.3. Demographics and Baseline Characteristics

Demographics and baseline characteristics will be summarized for subjects in the ITT population.

8.3.4. Efficacy Analyses

The analysis population is all randomized subjects to reflect the intent-to-treat (ITT) principle for all analyses.

8.3.4.1. Primary Endpoint Analysis

The primary estimand is intended to provide a population level estimate of the treatment effects of the pamrevlumab on a continuous endpoint, regardless of participants compliance with the IP dosing. Under an estimand framework, the analysis of primary endpoint includes the following components:

Population: Male and female patients aged 40 to 85 years, inclusive at screening initiation with IPF diagnosis made within 7 years prior to screening under American Thoracic Society/European Respiratory Society (ATS/ERS) criteria (Raghu 2018), and not currently receiving treatment with the 2 approved antifibrotic standard of care medications. All subjects in ITT population will be included.

Endpoint: Change from baseline in FVC (L) assessment at Week 48.

Treatment of interest: The randomization study treatment (pamrevlumab or placebo).

Handling of intercurrent events: The treatment policy strategy will be adopted for primary analysis. Details on handling missing values will be defined in a Statistical Analysis Plan (SAP).

Population-level summary for the endpoint: Absolute LSMMeans difference between pamrevlumab and placebo in change from baseline to Week 48 in FVC (L) estimated from a random coefficient model (RCM), the primary analysis approach. RCM model includes treatment, visit (as a continuous variable), visit-by-treatment interaction, randomization stratification factor, baseline FVC volume, age, sex, height as fixed effects, and the intercept and linear slope of visit as random effects. Details of RCM model will be defined in the SAP.

Additional sensitivity and supplemental analyses on primary endpoint will be defined in the SAP. The following analysis will be performed including, but not limited to:

1. With alternative model using quadratic assumption of FVC decline
2. Alternative assumptions for missing data (imputation method):
 - a. Missing not at random: Pattern mixture model (e.g., control-based imputation)
 - b. Missing not at random: Tipping point analysis (e.g., delta-adjusting pattern imputation)

